#### 1.5 Potential Risks and Benefits

Seven-hundred fourteen patients (excluding 13 patients from a company-sponsored, non-US IND study in Japan) have been treated with alisertib as of 29 March 2012. Clinical safety data includes experience from patients who received multiple cycles followed by treatment-free periods between each cycle, and from patients who reduced or discontinued treatment. Based on the available clinical data, drug abuse, dependency, and drug withdrawal effects were not observed.

To date, the observed risks associated with alisertib treatment, as detailed in the Safety Management Attachment of the IB, include: (1) reversible myelosuppression including leukopenia, neutropenia, febrile neutropenia, lymphopenia, thrombocytopenia, and anemia; (2) GI toxicity including stomatitis/mucositis/oral pain, nausea, vomiting, anorexia, abdominal pain, dyspepsia, diarrhea, and dehydration; (3) sedation, somnolence, confusional

state, disorientation (and associated memory loss), and gait disturbances; (4) alopecia; (5) asthenia/fatigue; (6) fever, (7) infection, (8) abnormal liver function tests (including aspartate transaminase [AST], alanine transaminase [ALT], bilirubin, alkaline phosphatase [ALP], and gamma glutamyl transferase [GGT]), and (9) rash, which may include bullous dermatitis, and palmar-plantar erythrodysaesthesia syndrome. While these toxicities are potentially associated with risk or discomfort to the patient, they are anticipated to be reversible.

To mitigate the inherent risks in clinical studies of alisertib, patients are evaluated frequently while they are receiving treatment.

Because alisertib inhibits Aurora A kinase, it is possible that alisertib may interfere with cancer growth and cause cancer cell death. Preclinical results indicate that alisertib is not a major substrate for efflux mechanisms that have been associated with cross-resistance between some types of anticancer agents. Thus, alisertib has potential through a potentially non-cross resistant pathway as compared to other agents the patients may have received. The clinical utility of these effects will be investigated in current and future studies.

This study will be conducted in compliance with the protocol, applicable regulatory requirements, and International Conference on Harmonisation (ICH) Good Clinical Practice (GCP), guidelines.

#### 1.6 Study rationale and selection of drug doses

#### **Study Rationale**

There are 3 subtypes of aurora kinases (A, B, C), but only aurora kinase A and B are potential therapeutic targets. Aurora kinase A inhibition leads to mitotic delay, monopolar spindles, and chromosomal segregation errors whereas aurora kinase B inhibition causes dysfunctional cytokinesis, polyploidy, and apoptosis. Preclinical studies have strongly suggested aurora kinases to be a relevant therapeutic target in mesothelioma patients. Several independent groups have reported that aurora kinase gene expression is upregulated in mesothelioma tumor tissue and is a negative prognostic factor.[15, 16](also our group – publication pending). Crispi et al.[17] have also shown that inhibition of mesothelioma cell lines with an aurora kinase inhibitor ZM447439 led to cell growth arrest and was target specific. Kim et al. also reported on irradiated mesothelioma cells and how inhibition of surviving and aurora kinase B resulted in mitotic cell arrest.

There are several aurora kinase inhibitors under investigation. For aurora kinase A inhibitors, alisertib, (MLN8237, Millenium) are under investigation in phase I and II trials. Preliminary results suggest dose limiting toxicity to be myelosuppression and mucositis. Aurora kinase B inhibitors, GSK1070916A (GlaxoSmithKline) and AZD1152 (AstraZeneca) are also under investigation in phase I and II trials in solid tumors and AML.

Several additional phase I and II trials of pan-aurora kinase inhibitor trials are underway in solid tumors. Alisertib (International Proprietary Name, also known as MLN8237) is a selective small molecule inhibitor of Aurora A kinase that is being developed for the treatment of advanced malignancies.

To date, there are no aurora kinase inhibitor-specific mesothelioma trials and the proposed study would be the first to assess this class of drug in the disease. Based on the preclinical data reported in the literature and our own profiling studies, we believe that aurora kinase is a feasible and relevant target in mesothelioma therapeutics. Alisertib is a novel compound that has a reasonable safety profile and may show efficacy in this population of patients.

### 1.6.1. Selection of Drug Dosages

The alisertib dose employed in this study will be 50 mg po BID (enteric coated tablet ECT) for 7 days then a 2 week treatment free period for a 21-day cycle. BID doses should be taken at least over 6 hours apart. This phase II dosing was established from phase I studies detailed in Section 1.3.

#### 2. STUDY OBJECTIVES

#### 2.1 Primary Objective

The primary objective of this study is to:

• To assess the 4-month disease control rate (DCR) in pre-treated patients with unresectable malignant pleural mesothelioma (MPM) treated with alisertib.

### 2.2 Secondary Objectives

The secondary objectives of this study are:

- To assess the response rate (confirmed and unconfirmed complete + partial responses)
- To assess the progression-free survival
- To assess overall survival.
- To evaluate the side effects and toxicities associated with this treatment regimen.
- To collect archival tissue, blood, pleural effusion fluid and plasma for correlative studies.

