#### 3.2.1 Inclusion Criteria

Each patient must meet all of the following inclusion criteria to be enrolled in the study:

- Voluntary written informed consent before performance of any study-related procedure not part of normal medical care, with the understanding that consent may be withdrawn by the subject at any time without prejudice to future medical care.
- Female subject is either:
  - o post-menopausal for at least one year before the screening visit, or
  - o surgically sterilized, or
  - willing to use an acceptable method of birth control (ie, a hormonal contraceptive, intra-uterine device, diaphragm with spermicide, condom with spermicide, or abstinence) for the duration of the study and at least 1 month after the last dose of alisertib.
- Male subject, even if surgically sterilized (ie, status postvasectomy), agrees to use an acceptable barrier method for contraception (condom with a spermicidal agent), or completely abstain from heterosexual intercourse during the entire study treatment period through 4 months after the last dose of alisertib.
- Absolute neutrophil count (ANC) > 1500/mm³, platelets > 100,000/mm³, Hgb > 9 g/dL. Total bilirubin ≤ 1.5 x upper limit of nomal (ULN), SGOT (AST) and SGPT (ALT) < 2.5 x ULN. AST and/or ALT may be up to 5X ULN if with known liver mets

- Adequate renal function as defined by: Calculated creatinine clearance must be ≥ 30 mL/minute(see Cockcroft-Gault formula in Section 9.5)
- Eastern Cooperative Oncology Group (ECOG) performance status 0-2 (refer to Section 9.4)
- Pathologic diagnosis of malignant mesothelioma (any primary site is acceptable)
- Have unresectable malignant mesothelioma (any histology)
- Received at least one prior pemetrexed-based chemotherapy for unresectable disease, unless within 3 months of receiving platinum-pemetrexed therapy for neoadjuvant or adjuvant treatment that has been unsuccessful.

- Up to 4 prior lines of systemic therapy (biologic or chemotherapy) are allowed. Maintenance therapy after 4-6 cycles of front-line chemotherapy is still considered 1 line of therapy and is not considered 2 separate therapies.
- Patients must have measurable disease by modified RECIST or RECIST.
   Examinations for assessment of measurable disease must have been completed within 28 days prior to registration.
- Patient must be >/= 18 years of age

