#### 3.10 Efficacy and Safety Measurements

#### 3.10.1 Efficacy Measurements

Patients will be re-staged every 2 cycles of therapy (6 weeks). 1 cycle = 21 days or 3 weeks. Imaging studies will consist of any of the following studies: PET-CT scans, chest CT scans, abdominal-pelvic CT scans. Modified RECIST (preferred) or RECIST (if modified RECIST cannot be used) measurements will be performed after every 2 cycles of therapy. The radiologist or the PI will review and determine response based on the RECIST. Examples of these measurements are described in Tsao et al.[1]

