## **5.4** Evaluation of Efficacy

Patients will be re-staged every 2 cycles of therapy. 1 cycle = 21 days or 3 weeks. Imaging studies will consist of *any* of the following studies: PET-CT scans, chest CT scans, abdominal-pelvic CT scans. Modified RECIST (preferred) or RECIST (if modified RECIST cannot be used) measurements will be performed after every 2 cycles of therapy. The radiologist or the PI will review and determine response based on the RECIST and the data will be documented in the Case Report Form (CRF). Examples of these measurements are described in Tsao et al.[1]

The primary objective of this study is to assess the efficacy of alisertib in pretreated patients with unresectable malignant mesothelioma (pleural or peritoneal). The primary endpoint is the disease control rate at 4 months in patients with unresectable malignant pleural mesothelioma (MPM) treated with alisertib. The trial will be conducted by the Simon's minimax two-stage design and the disease control rate at 4 months will be estimated accordingly (Simon, 1989).

Standard RECIST measurement definitions will be used.

Complete Response (CR): Complete disappearance of all measurable and non-measurable disease. No new lesions.

Partial Response (PR): Greater than or equal to 30% decrease under baseline of the sum of longest diameters of all target measurable lesions. No unequivocal progression or non-measurable disease. No new lesions.

Stable disease (SD): Does not qualify for CR or PR or Progression.

Progression (PD): One or more of the following must occur: 20% increase in the sum of longest diameters of target measurable lesions over smallest sum observed (over baseline if no decrease during therapy). Unequivocal progression of non-measurable disease in the opinion of the treating physician (an explanation must be provided). Appearance of any new lesion/site. Death due to disease without prior documentation of progression and without symptomatic deterioration.

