#### **5.6** Correlative Studies

Blood Specimens will be collected at baseline (pretreatment), cycle 3 – day 1 and at progression and banked at MD Anderson Cancer for subsequent analysis. At each time

point, blood will be collected into three (3) x 8 mL EDTA Vaccutainer top tubes separated; plasma and buffy coat will be collected and stored at -70 until analysis.

Pleural Effusion Fluid: in cases when pleural effusion fluid is available, a 10 mL aliquot of the pleural effusion fluid will be collected in a sterile container, aliquoted and stored at -70C until analysis.

Patients must have either archived baseline tumor specimens available and adequate for biomarker analysis or must undergo a tumor tissue biopsy. Tumor specimens will be batched until the end of the clinical trial and subsequently evaluated for aurora kinase pathway molecules by immunohistochemistry, fluorescent in situ hybridization (FISH) for c-myc gene amplification, and next-generation sequencing. Correlation of biomarkers to patient demographics and clinical outcome will be analyzed by the below statistical analysis.

Descriptive statistics including mean, standard deviation, median, and range will be provided for continuous variables such as age. Frequency tables will be used to summarize categorical variables such as gender, and response. The standard error and confidence interval on estimating the disease control rate will be provided. The distribution of time-to-event endpoints, such as time to progression and overall survival, will be estimated using the method of Kaplan and Meier. Comparison of time-to-event endpoints by important patient characteristics will be made using the log-rank test. Cox proportional hazard regression will be employed for multi-covariate analysis on time-to-event outcomes when appropriate.

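### The partial-response rule in Section 5.4, read literally, denies PR to anyone with persisting non-measurable disease, and the response rate is planned only as a pooled figure with no definition of confirmation

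*Combined protocol and SAP*

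**What the plan says.** **Response rate.** The Protocol Summary, Section 2.2 and Section 5.1 give the same first secondary objective: "To assess the response rate (confirmed and unconfirmed complete + partial responses"). Confirmed is not defined, no confirmation interval is set, and no separate confirmed rate is planned. The CR and PR criteria in Section 5.4 contain no repeat-scan step.

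**Scans and readers.** Section 3.10.1: "Patients will be re-staged every 2 cycles of therapy (6 weeks"). Section 5.4: "The radiologist or the PI will review and determine response based on the RECIST". No independent review is stated.

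**PR rule.** After the 30% criterion for target lesions, Section 5.4 adds "No unequivocal progression or non-measurable disease. No new lesions". The progression rule in the same section reads "Unequivocal progression of non-measurable disease in the opinion of the treating physician". Above both stands "Standard RECIST measurement definitions will be used".

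**Entry.** Section 3.2.1: "Patients must have measurable disease by modified RECIST or RECIST". Additional non-measurable disease is not an exclusion.

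**The concern.** There are two separate defects in how the first secondary endpoint is specified.

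First, the PR sentence makes the absence of non-measurable disease a condition of partial response. A patient whose target lesions shrink by 30% or more, but who still has some non-measurable disease, then meets neither CR nor PR and falls to stable disease by default. An assessor who applied the sentence as written would lose genuine partial responders.

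Second, the objective names two kinds of response and gives no rule for telling them apart. An analyst could not later separate them by a pre-specified criterion, and a response seen on one scan counts the same as one that was repeated. The trial has no control arm to absorb measurement error, and the reader may be the PI. Section 5.6 also tabulates response in the biomarker work, so spurious responders would add noise there.

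At stake are the meaning and reproducibility of a descriptive secondary figure. The go/no-go decision is not at stake.

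**Working it through.** **1. The definitions in Section 5.4, side by side**

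| Category | Condition on non-measurable disease |
|---|---|
| CR | All of it has disappeared |
| PR, as worded | No unequivocal progression, *or* no non-measurable disease, under one shared *No* |
| PD | Unequivocal progression *of* it |
| SD | Whatever is not CR, PR or progression |

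Read literally, PR requires non-measurable disease to be absent, which repeats part of the CR condition. With *of* in place of *or*, PR becomes the mirror image of the PD rule. The section's own structure therefore points to *of*.

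**2. Is the primary design touched?** The documents give no planning figure for the response rate, so the only stated figures to reproduce are those of the Simon design in Section 5.1 (7/24, then 21/53). With X1 ~ Bin(24, p) and X2 ~ Bin(29, p):

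- P(stop early) = P(X1 ≤ 7)
- P(accept) = Σ over x from 8 to 24 of P(X1 = x)·P(X2 ≥ 22 − x)
- E(N) = 24 + 29·[1 − P(stop early)]

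| | p = 0.30 | p = 0.50 | Stated |
|---|---|---|---|
| P(stop early) | 56.5% | 3.2% | 57%, 3% |
| P(accept) | 0.0466 | 0.9017 | at most 0.05; at least 0.90 |
| E(N) | 36.6 | 52.1 | 36.6, 52.1 |

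All are reproduced. The rule counts patients alive and progression-free at 4 months. CR, PR and SD all qualify, so moving a patient between PR and SD, or between confirmed and unconfirmed, changes none of these figures.

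**3. How many single-scan responses could be noise?** The documents give no measurement error, so this rests on assumptions: tumours that do not change, independent normal error of SD σ on the log scale at baseline and at each scan, and three scans (weeks 6, 12 and 18). A spurious response is log(scan/baseline) ≤ ln 0.7 = −0.357. For one scan the probability is Φ(−0.357/(σ√2)); at σ = 0.15 this is Φ(−1.68) = 4.6%. For three scans, simulating 1,000,000 tumours gives:

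| σ | Any of 3 scans | × 53 | Two consecutive scans | × 53 |
|---|---|---|---|---|
| 0.05 | about 0% | 0 | about 0% | 0 |
| 0.10 | 1.6% | 0.8 | 0.1% | 0.06 |
| 0.15 | 11.1% | 5.9 | 1.8% | 0.9 |

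Stopping follow-up at an apparent 20% rise over the smallest sum, as the PD rule implies, changes little: 1.6% and 10.5% on any scan, and 0.1% and 1.7% on two consecutive scans, at σ = 0.10 and 0.15.

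**4. Is the upper end plausible?** Under the same model, the 20%-over-nadir rule would falsely call about 37% of unchanged tumours progressed within three scans at σ = 0.10, 60% at 0.15 and 72% at 0.20. Error of 0.15 would thus damage the primary endpoint far more than the response rate. I treat it as an outer bound and do not carry 0.20 into the range (there the response figures are 22.5% and 5.2%).

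**5. What this does to a reported rate (illustration).** Assume 5 pooled responses in 53, all PRs: 5/53 = 9.4% (exact 95% CI 3.1 to 20.7).

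- If 2 of the 5 are unconfirmed, the confirmed rate is 3/53 = 5.7% (1.2 to 15.7).
- If instead the PR sentence is applied literally and 3 of the 5 have non-measurable disease, the pooled rate is 2/53 = 3.8% (0.5 to 13.0).

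**The case against.** **Pooling is openly declared.** Three sections state the same definition, and no threshold, test or decision hangs on it. This stands: the pooled rate is correct for what it claims to be, and replacing it with a confirmed-only rate would be a preference. What remains is that confirmed is undefined and no separate line is promised.

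**The PR sentence is probably a one-letter slip.** The standard-RECIST sentence and the PD rule in the same section both point to the intended meaning, and the slip could even come from the conversion of the PDF to text. This largely stands. Harm arises only if someone applies the words literally, so the original file should be checked first. If the slip is in the original, an operative definition that contradicts its own stated standard should still be corrected.

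**The effect size is assumed.** This stands. The model also gives every patient three scans. Patients who progress leave treatment, and under the null only 30% are progression-free at 4 months, so many would have fewer scans. With one scan at σ = 0.15, the 4.6% is 0.046 × 53 = 2.4 patients.

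**Stronger readings the documents do not support.**

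- A reader might infer that the response rate will be wrong in both directions, or is unreliable. One direction is a declared choice and the other a hypothetical misreading; they do not carry equal weight.
- A reader might infer bias against the 3% to 30% chemotherapy range in Section 1.1. That range is background. No comparison is planned, and the text does not say whether those responses were confirmed.
- A reader might infer that effusions will be scored as non-measurable disease. Section 5.6 speaks of fluid "in cases when pleural effusion fluid is available" only for specimen banking.

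**Conclusion.** The point holds as a minor one, in two parts. The PR rule in Section 5.4 is internally inconsistent and, taken literally, would reclassify some partial responders as stable. The response rate is planned only in pooled form with no definition of confirmation, so it may include responses that the next scan would not uphold; a confirmed rate would be equal or lower.

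The documents do not fix the size. Under the assumptions stated (unchanged tumours, independent error, log-SD 0.05 to 0.15, three scans each), spurious responders in 53 run from about 0 to 6 on any single scan and about 0 to 1 on two consecutive scans. The top of that range needs an error level that would trouble the primary endpoint first. The loss from the PR wording depends on how many responders have non-measurable disease and on whether the sentence is applied literally; neither is known. The 4-month disease control rate, the 7/24 and 21/53 rules and the sample size do not change.

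**What to change.** - **Section 5.4, PR rule:** check the original file and, if the slip is there, replace *or* with *of*, so that the condition is the absence of unequivocal progression of non-measurable disease.
- **Protocol Summary and Sections 2.2, 5.1 and 5.4:** keep the declared pooled rate and add the confirmed rate on its own line. Define confirmed as criteria met again at the next scheduled 6-week restaging. Responders with no later scan, for example because they stopped for toxicity or withdrew, count as unconfirmed and stay in the denominator.

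**Cost:** an amendment to wording and one extra table line. No scans or patients are added. The confirmed rate will be equal to or lower than the pooled rate, and because responders who stop early count as unconfirmed it may understate durable response slightly. Showing both lines lets the reader see this.

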#### 2.3 Exploratory Objectives

- To collect archival or new tissue, blood and pleural effusion fluid for correlative studies. Tissue biomarkers to be evaluated include aurora kinase pathway and c-myc gene amplification.
- Next generation sequencing (NGS) will be conducted on adequate tumor tissue specimens.

#### 3. INVESTIGATIONAL PLAN

This is an investigator-initiated study. The principal investigator, [name], is conducting the study.

#### 3.1 Overall Design and Plan of the Study

This is a standard single-arm, single institution phase II trial that will enroll patients with malignant mesothelioma and treat them with alisertib monotherapy. The patients will be monitored for efficacy by either modified RECIST (preferred) or RECIST criteria (if modified RECIST cannot be performed) every 6 weeks. Patients with disease progression by either modified RECIST or RECIST criteria will be taken off active treatment from the trial and begin long-term follow-up.

The primary endpoint is 4-month disease-control rate. Secondary and exploratory endpoints include response rates, progression-free survival, overall survival, safety/toxicity profile, and collection of archival or fresh tissue and blood for correlative studies (See Section 5.6).

The alisertib dose employed in this study will be 50 mg po BID (enteric coated tablet ECT) for 7 days then a 2 week treatment free period for a 21-day cycle. BID doses should be taken at least over 6 hours apart.

Enrollment is defined as the first day of alisertib treatment (ie, Day 1 of Cycle 1).

Evaluable patients are defined as completing at least 1 cycle of alisertib treatment and having a documented radiographic response.

Radiographic assessments will occur every 6 weeks using modified RECIST (preferred) or RECIST (if modified RECIST is not feasible).

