#### **Number of Patients**

53 eligible patients, 58 maximum patients (assumes 5 inevaluable patients)

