#### **Statistical Procedures**

The primary objective of this study is to assess the efficacy of alisertib in pretreated patients with unresectable malignant mesothelioma (pleural or peritoneal). The primary endpoint is the disease control rate at 4 months in patients with unresectable malignant pleural mesothelioma (MPM) treated with alisertib. The trial will be conducted by the Simon's minimax two-stage design and the disease control rate at 4 months will be estimated accordingly.[2]

It is assumed that the new regimen will have a target disease control rate of 50% at 4 months. A disease control rate of 30% or lower is considered a failure and the new regimen will be rejected under this circumstance. When the probability of accepting a "bad" regimen (i.e. disease control rate<=30%) is 0.05 and the probability of rejecting a "good" regimen

(i.e. disease control rate >=50%) is 0.10, Simon's minimax design requires to enter 24 patients in the first stage. If 7 or less patients are alive and free of disease progression to the treatment at 4 months, the trial will be stopped and the regimen will be declared as ineffective. If there are 8 or more patients are alive and progression-free at 4 months, 29 more patients will be entered in the study to reach a total of 53 patients. By the end of the study, the new regimen will be rejected if disease control rate is less than or equal to 21/53 and will be accepted otherwise. The operating characteristics of the trial are given as follows. When the true disease control rate is 0.30 the probability of stopping the trial early is 57%. On the other hand, if the true disease control rate is 0.50, the probability to stop the trial early is 3%. The expected sample sizes are 36.6 and 52.1 when the true response rates are 0.3 and 0.5, respectively.

This design has the minimax property of minimizing the maximum sample size under null hypothesis. If the number of disease control required for moving the trial to the second stage has not been achieved, the patient enrollment will be halted until enough responses observed.

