#### 3.2 Selection of Patients

The total number of patients to be enrolled on this study is 58 subjects for 53 evaluable patients.

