### 5. STATISTICAL PROCEDURES

## 5.1 Study Design and Overview of Primary and Secondary Endpoints

The primary objective of this study is to:

• Assess 4-month disease control rate (DCR) in pre-treated patients with unresectable MPM treated with alisertib

The secondary objectives of this study are to:

- To assess the response rate (confirmed and unconfirmed complete + partial responses)
- To assess the progression-free survival.
- To assess overall survival.
- To evaluate the side effects and toxicities associated with this treatment regimen.
- To collect archival tissue, blood, pleural effusion and plasma for correlative studies.

The primary endpoint is the disease control rate at 4 months in patients with unresectable malignant pleural mesothelioma (MPM) treated with alisertib. The trial will be conducted by the Simon's minimax two-stage design and the disease control rate at 4 months will be estimated accordingly (Simon, 1989)

It is assumed that the new regimen will have a target disease control rate of 50% at 4 months. A disease control rate of 30% or lower is considered a failure and the new regimen will be rejected under this circumstance. When the probability of accepting a "bad" regimen (i.e. disease control rate<=30%) is 0.05 and the probability of rejecting a "good" regimen (i.e. disease control rate >=50%) is 0.10, Simon's minimax design requires to enter 24 patients in the first stage. If 7 or less patients are free of disease progression to the treatment at 4 months, the trial will be stopped and the regimen will be declared as ineffective. If there are 8 or more patients are alive and progression-free at 4 months, 29 more patients will be entered in the study to reach a total of 53 patients. By the end of the study, the new regimen will be rejected if disease control rate is less than or equal to 21/53 and will be accepted otherwise. The operating characteristics of the trial are given as follows. When the true disease control rate is 0.30 the probability of stopping the trial early is 57%. On the other

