# 5.2 Sample Size Estimation/Accrual Rate

It is anticipated to accrue 1-2 patients per month.

Sample size = 53 evaluable patients, 58 maximum patients (estimating 5 inevaluable patients)

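### The 53 patients of the primary decision rule carry three different labels (entered, evaluable, eligible), and under the evaluable label early failures can drop out of the denominator

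*Combined protocol and SAP*

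**What the plan says.** The decision rule stands in Section 5.1 and in the summary's Statistical Procedures. Stage 1 enters 24 patients and stops at 7 or fewer successes. Otherwise "29 more patients will be entered in the study to reach a total of 53 patients", and at the end "the new regimen will be rejected if disease control rate is less than or equal to 21/53". No analysis population is named, and Section 5.7 only refers back to 5.1.

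The 53 is labelled differently elsewhere:

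- Section 3.2: "The total number of patients to be enrolled on this study is 58 subjects for 53 evaluable patients".
- Section 5.2: "Sample size = 53 evaluable patients, 58 maximum patients (estimating 5 inevaluable patients".
- Protocol Summary, Number of Patients: "53 eligible patients, 58 maximum patients (assumes 5 inevaluable patients".

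Section 3.1 supplies two definitions: "Enrollment is defined as the first day of alisertib treatment (ie, Day 1 of Cycle 1", and "Evaluable patients are defined as completing at least 1 cycle of alisertib treatment and having a documented radiographic response". Restaging is every 6 weeks (3.1, 3.10.1), and the Schedule of Events puts the first on-study scan in week 3 of Cycle 2. Section 5.4 counts as progression a death from disease that had no earlier documented progression and no symptomatic deterioration.

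**The concern.** Because enrolment is the first dose, the 58 enrolled in 3.2 are all treated. A total of 53 entered and a total of 58 enrolled cannot then both hold unless the words refer to different sets of patients, and no section says which set the rule counts. Only the 53 carries all three labels. The 24 is only ever described as entered, and inherits the ambiguity as the first part of the 53.

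The labels select different patients. Evaluability needs a completed cycle and a radiographic record, so a treated patient who dies, deteriorates or stops before the first scan can be inevaluable. Section 5.4 would make some of these deaths progression events while 3.1 removes the same patients from the count. The trial has no control arm and is judged against a fixed 30%, so removing early failures raises the observed rate without any change in the drug's effect.

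The decision itself can turn on this. Suppose 58 are treated, 53 are evaluable, 22 succeed and the five inevaluable patients do not. The evaluable reading accepts, at 22/53 = 41.5%. The same 22 are 22/58 = 37.9% of treated patients, below 21/53 = 39.6%. Counting the first 53 treated would also reject if any of the 22 successes fell among the last five treated.

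**Working it through.** **Inputs.** From 5.1: null rate 0.30, target 0.50, error limits 0.05 and 0.10, stage 1 rule 7/24, final rule 21/53. From 5.2: 5 inevaluable of 58, so f = 5/58 = 0.0862. Not in the documents, and therefore varied: the share s of inevaluable patients who are failures at 4 months.

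**The plan's own figures.** The acceptance probability at true rate p is the sum over x = 8 to 24 of P(X1 = x) × P(X2 ≥ 22 − x), with X1 ~ Bin(24, p) and X2 ~ Bin(29, p).

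- p = 0.30: early stopping 0.5647, alpha 0.0466, expected size 24 × 0.5647 + 53 × 0.4353 = 36.6.
- p = 0.50: early stopping 0.0320, power 0.9017, expected size 52.1.

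These agree with 5.1, apart from 0.5647 being given as 57%. A search confirms 7/24, 21/53 as the minimax design. The design arithmetic is sound; the question is whom it counts.

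**Evaluable reading, 30% true in all treated patients.** The rate among evaluable patients is pe = (0.30 − f(1 − s)) / (1 − f). For example:

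- s = 0.8: (0.30 − 0.0172)/0.9138 = 0.3094.
- s = 1.0: 0.30/0.9138 = 0.3283.

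With each patient independently evaluable with probability 53/58, 58 treated patients yield at least 53 evaluable with probability 0.616. The chance of falling short at the 58 maximum is therefore about 38%, and the plan has no rule for that case. Three conventions were run: 53 evaluable always reached; a cap of 58 treated with 22 successes still required; and a cap of 58 with the observed rate required to exceed 21/53. In the capped runs, stage 1 is read at the 24th evaluable patient.

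| Failure share s | pe | Alpha, 53 always reached | Alpha, cap 58, 22 successes | Alpha, cap 58, rate above 21/53 |
|---|---|---|---|---|
| 50% | 0.281 | 0.023 | 0.020 | 0.028 |
| 60% | 0.291 | 0.033 | 0.029 | 0.039 |
| 70% | 0.300 | 0.047 | 0.040 | 0.054 |
| 80% | 0.309 | 0.064 | 0.055 | 0.072 |
| 90% | 0.319 | 0.085 | 0.074 | 0.095 |
| 100% | 0.328 | 0.110 | 0.097 | 0.122 |

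Alpha crosses 0.05 at s of about 72%, 77% and 68% in the three columns. At s = 100%, early stopping under the null falls from 56% to 44%.

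The 70% row also covers two neutral cases: inevaluability unrelated to outcome, and a 30% null that was set for evaluable patients. In both, pe = 0.30. Alpha is 0.047 only if 53 evaluable are always reached, and 0.040 or 0.054 under the cap.

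**All-treated reading, 50% true in evaluable patients only.** The all-treated rate is 0.50(1 − f) + f(1 − s), which gives 0.483, 0.474, 0.466 and 0.457 at s = 70%, 80%, 90% and 100%. Power under 7/24, 21/53 is then 0.853, 0.823, 0.790 and 0.753.

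**The case against.** The strongest reply is that one reading fits all the numbers: 58 dosed, 5 lost to evaluability, 53 counted. Section 5.2 belongs to the statistical chapter and says evaluable. The summary also subtracts 5 inevaluable patients from 58, so eligible there is probably a loose word. This stands as the likeliest intent. A reader might infer from the word entered, together with the definition of enrolment, that the rule is meant for all treated patients. The documents do not support that firmly, since entered is never defined. Accepting the evaluable reading does not remove the problem, however, because it is the reading under which early failures can leave the count.

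A reader might also take *radiographic response* literally, so that stable and progressive disease would be inevaluable. A documented response assessment is more plausibly meant, and nothing here rests on the literal reading.

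A second reply is that the harm is conditional. That is correct. The documents do not say whether the 30% describes treated or evaluable patients, nor how inevaluable patients fare. Section 3.8 keeps patients who stop treatment in follow-up for progression and survival, so some inevaluable patients may be progression-free at 4 months.

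A third reply is that merely naming the evaluable population in 5.1 would end the contradiction. It would end the conflict of wording, but would leave early failures outside the denominator and a shortfall below 53 without a rule.

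**Conclusion.** The conflict is in the text and should be resolved before the stage 1 count is read. The same 53 is a number entered, a number evaluable out of 58, and a number eligible, and the rule names no population.

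The effect on error rates depends on assumptions. With the evaluable reading, a 30% null for all treated patients and 5/58 inevaluable, alpha ranges from 0.064 to 0.110 at failure shares of 80% to 100% when 53 evaluable are always reached. Across the two capped conventions it ranges from 0.055 to 0.122. Below about 72%, 77% or 68%, depending on the convention, alpha is under 0.05.

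Two stronger conclusions might be drawn and are not supported. The first is that the trial's type I error is 11%: that is the 100% extreme of one convention. The second is that inflation begins only once inevaluable patients fail more often than the 70% null failure rate: under the cap with a rate-based rule, alpha is already 0.054 at exactly 70%.

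**What to change.** In 3.1, 3.2, 5.1, 5.2 and the summary, use one population and one word for it:

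- Apply 7/24 and 21/53 to the first 24 and first 53 eligible patients who receive at least one dose.
- Count as a failure any patient who progressed, died, or has no evidence of being alive and progression-free at 4 months.
- Replace only patients found to be ineligible.
- Report the rate in evaluable patients as a sensitivity analysis, listing each exclusion and its reason.
- State which population the 30% and the 50% describe.

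**Cost.** If both rates describe all treated patients, alpha stays at 0.047 and power at 0.902. The text changes and inevaluable patients are no longer replaced. The reported rate will be slightly less favourable than the evaluable rate if inevaluable patients mostly fail. If the 50% describes evaluable patients only, the plan should state the lower power: 0.853, 0.823, 0.790 or 0.753 at failure shares of 70%, 80%, 90% or 100% among 5/58 inevaluable. No larger sample is requested.
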